Appendix #1

Appendix 1. Frequency of Outcomes for Aims 1 – 3.

Assessment Category #=with and without stim	Assessments	Pre-screen	Screen	Pre-Usual Care	Pre-implant	Post-Implant/ Pre-Intervention	Weekly	Periodic Through Intervention	Monthly	Post-Intervention #1	Post-Intervention #2	Follow Up(s)
Medical	SC MRI	X	or X									
	ASIA		X	X	X					X	X	
	Physician and PT Medical		X	X	X					X	X	X
	Pregnancy	X	X									
	Blood Work		X	X	X					X	X	X
	Drug Testing	X	X	X	X	X	X	X		X	X	X
Voluntary	MMR		X									
	FNPA		X	X	X	X#				X#	X#	X#
	NRS trunk and leg score		X	X		X#		X#		X#	X#	X#
	Lower Extremity Torque with EMG					X#		X#		X#	X#	X#
	Neuromuscular Voluntary Movement Assessments					X#		X#		X#	X#	X#
Cardiovascular	Ambulatory BP monitoring		X	X				X	X	X	X	X
	Ambulatory HR monitoring		X	X				X	X	X	X	X
	12 lead ECG				X					X	X	
	Orthostatic Stress Test		X	X	X	X#		X#		X#	X#	X#
	Vascular Ultrasound			X	X	X#		X#		X#	X#	X#
	Echo-cardiography		X	X	X	X#		X#		X#	X#	X#
	Arterial pulse wave velocity		X	X	X	X#		X#		X#	X#	X#
	Sympathetic skin responses				X					X	X	
Stand	Dexa		X		X					X	X	X
	Independence levels during stand -			X	X	X#	X#	X#		X#	X#	X#
	Standing Assessments				X	X#		X#		X#	X#	X#
Respiratory	Pulmonary Function Test		X		X	X#				X#	X#	X#
	Respiratory Motor Control Assessment		X		X	X#				X#	X#	X#
	Resting metabolic rate		X	X	X					X	X	X

Assessment Category #=with and without stim	Assessments	Pre-screen	Screen	Pre-Usual Care	Pre-implant	Post-Implant/ Pre-Intervention	Weekly	Periodic Throughout Intervention	Monthly	Post-Intervention #1	Post-Intervention #2	Follow Up(s)
Bladder	Urodynamics		X	X	X					X	X	X
	Bladder Questionnaire			X	X					X	X	X
	Urinalysis			X	X					X	X	X
	Ultrasound			X	X					X	X	X
Bowel	Bowel Questionnaire			X	X					X	X	X
	Anorectal Manometry			X	X					X	X	X
Sexual Function	International Dataset (Males)			X	X					X	X	X
	International Dataset (Females)			X	X					X	X	X
Quality of Life	SCI-QOL		X		X					X	X	X
	SCI-FI		X		X					X	X	X
	PROMIS		X		X					X	X	X
	EQ-5D-3L		X		X					X	X	X

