The potential research participant will be assessed for medical eligibility by the research team's neurosurgeon, cardiologist and study physician. The study physician will conduct a medical history and physical examination and determine medical eligibility based on the clinical inclusion criteria (#1-4, see section IV.A below) and exclusion criteria (#1-6, see section IV.A below) and consideration of the risk assessment specific for the individual based on their medical history and examination. Following medical clearance for the assessments and participation in the screening portion of the study by the study physician, the potential research participant will undergo behavioral, neurophysiological, and cardiovascular assessments (Appendix #1). Pre-usual care assessments may also be done during the screening visit to reduce the number of study visits for participants who do not live locally. Potential study eligibility will be determined by the investigators based on the evaluation of these assessments to be consistent with the inclusion criteria (#5-9, see section IV.A below). The research participant will then be seen by the study cardiologist who will review the medical record and the cardiovascular assessments. The study neurosurgeon will then review their medical history and the MRI and provide a preliminary recommendation for surgical implantation. *Drug/Nicotine Testing:* The intent is to avoid nicotine users. If a potential research participant tests positive for nicotine during the screening period or the post-usual care/pre-implant assessments, they will be ineligible for the study. After implantation, we will conduct random nicotine testing using a urine sample and levels will be recorded. Nicotine testing will then be done daily until levels are negligible and then weekly for one month. If nicotine levels remain absent, testing will return to random testing. The individual will not be removed from the study after implantation but nicotine levels will be monitored and if detected, levels will be recorded.

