[name] and/or [name] will meet with the potential research participant at the end of the screening and review the results of the assessments and discuss their eligibility. If they are ineligible, the reasons will be explained and they will be asked if they would like to remain in the database for recruitment in future studies. If they are eligible, then all the potential risks will be discussed with them. They will be informed that if they are still interested in participating in the study the next phase is for them to continue with their current daily activities for at least 80 days without any intervention (Usual Care). In some cases an additional pregnancy test may be done if the pre-screen and screen time points are more than 6 months apart.

2. Usual Care (3rd Consent). If the individual is determined to be eligible for the Usual Care period of the study, as determined by the screening assessments, he/she will be consented for Usual Care. The Usual Care period will last for at least 80 days without any intervention and the participant will continue with his/her current daily activities. [name] will encourage the research participant to discuss the study with family, friends, and physicians during this period to facilitate their ability to reach the most informed decision regarding surgical implantation and full enrollment into the study. They will be informed that they are not consenting to surgical implantation – that consent would be signed when they return for the surgical implant and intervention phase of the study. They will also be informed that during the Usual Care phase of the study they can decide not to continue on with the study and let us know at any time. At the completion of the Usual Care phase of the study they will complete the post-usual care behavioral, cardiovascular, respiratory, bladder, bowel, and sexual function assessments (Appendix #1). If the individual meets all the inclusion and exclusion criteria, and is given medical clearance by the study from the cardiologist and the study physician and is recommended for possible implantation by the study neurosurgeon, then they will be enrolled in the study and randomized.

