Hypothesis 1a: Primary Efficacy Hypothesis: CV-scES will result in greater cardiovascular functional improvements than those achieved during Usual Care Intervention.

Hypothesis 1b: Secondary Efficacy Hypothesis: Task specific voluntary movement training using Vol-scES will result in greater improvements in voluntary movement than those achieved during Usual Care Intervention.

Hypothesis 1c: Secondary Efficacy Hypothesis: Stand Stand-scES (parameters optimized for standing) will result in greater improvements in the ability to stand than those achieved during the Usual Care Intervention.

Secondary Analyses:

Hypothesis 1d: Task specific voluntary movement training using Vol-scES (parameters optimized for voluntary movement) will result in more successful voluntary movements than CV-scES.

Rationale: We propose that the spinal circuitry is the key integrator of complex signals from the periphery and supraspinal centers that drive the final motor pool output. We predict that the circuitry is continuously adapting to activity-dependent events that functionally configure the spinal networks to optimize generation of a specific motor task. Other possibilities are that the scES retrogradely stimulates residual axons that anatomically cross the lesion but are not functional, or, that scES restores the conduction properties that are lost with demyelination or other consequences of damage [2, 70, 73-76]. If only the restoration of the conduction of the residual supraspinal connections are needed, then the scES **alone** without voluntary training should be sufficient to restore voluntary movement of the legs. However, if the spinal cord circuitry is a key controller, then task specific training of voluntary movement in the presence of scES would also be required to optimally generate voluntary movement.

Methods: Linear statistical models will be fit with coefficients relating to the three stimulation methods. This hypothesis will be tested by if the Vol-scES estimates are significantly higher than those for CV-scES or Stand-scES stimulation parameters. See Section G for details.

Hypothesis 1e: CV-scES (parameters optimized for cardiovascular function) will result in greater cardiovascular functional improvements than Vol-scES.

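### Appendix 1 omits ambulatory BP, ambulatory HR and NRS at Pre-implant, against the protocol text, so their change during Usual Care is not measured

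*Protocol*

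**What the plan says.** - **Schedule (Protocol, Appendix #1).** The rows "Ambulatory BP monitoring" and ambulatory HR monitoring are marked at Screen and Pre-Usual Care, then not again until the Periodic and Monthly columns. The row "NRS trunk and leg score" is marked at Screen and Pre-Usual Care, then at Post-Implant/Pre-Intervention with and without stimulation. None of the three is marked at Pre-implant.
- **Usual Care (Protocol III.B.2).** "The Usual Care period will last for at least 80 days without any intervention". At its end, "they will complete the post-usual care behavioral, cardiovascular, respiratory, bladder, bowel, and sexual function assessments", with a reference to Appendix #1.
- **Before implant (Protocol III.B.3).** The assessments that established eligibility for Usual Care are to be done again.
- **Screening (Protocol III.B.1.c).** "Pre-usual care assessments may also be done during the screening visit", so the two early recordings may fall at one visit.
- **Hypotheses (Protocol III.C, Specific Aim 1).** Hypothesis 1a, the primary one, expects "greater cardiovascular functional improvements than those achieved during Usual Care Intervention". Hypothesis 1b has the same form for voluntary movement.
- **Analysis (Protocol III.G).** Hypotheses 1a to 1c use paired t-tests of the end of the second intervention period against the baseline period.

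**The concern.** Change over Usual Care needs a value at each end of it. These three measures have up to two values at the start and none at the end. Site staff work from the schedule table, so they would not collect what the text promises, and a missed end-of-Usual-Care value cannot be recovered once the participant has been implanted.

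Ambulatory monitoring is the protocol's 24-hour, daily-life measure of blood pressure. Inclusion criterion 7 (IV.A) can be met by highly variable blood pressure over 24 hours, which is what this recording shows. A baseline taken at or near selection is therefore open to regression to the mean. It is also separated from the first training session by at least 80 days, surgery and 2-3 weeks of recovery. Any movement in that interval would count as an effect of scES.

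**Working it through.** **1. The schedule, row by row** (Appendix #1; X# means with and without stimulation). Each of the seven rows parsed (ambulatory BP, ambulatory HR, NRS, FNPA, orthostatic test, echocardiography and SCI-QOL) has exactly 11 cells for the 11 time-point columns. The blanks are therefore unlikely to come from a column shift in the text extraction.

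| Measure | Screen | Pre-Usual Care | Pre-implant | Post-Implant/Pre-Intervention |
|---|---|---|---|---|
| Ambulatory BP | X | X | blank | blank |
| Ambulatory HR | X | X | blank | blank |
| NRS | X | X | blank | X# |
| "Orthostatic Stress Test" | X | X | X | X# |
| Echocardiography | X | X | X | X# |
| Pulse wave velocity | X | X | X | X# |
| Vascular ultrasound | blank | X | X | X# |
| FNPA | X | X | X | X# |

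**2. What follows for each measure.**
- Ambulatory BP and HR: two marks before Usual Care, none at its end, none before intervention starts. Change during Usual Care cannot be calculated.
- NRS: the off-stimulation value at Post-Implant/Pre-Intervention is a later pre-training baseline. The change from Pre-Usual Care to that point is Usual Care plus surgery plus recovery, and the parts cannot be separated.
- Orthostatic test, echocardiography, pulse wave velocity, vascular ultrasound and FNPA: both ends of Usual Care are marked.

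**3. Text against table.** III.B.2 promises behavioral and cardiovascular assessments after Usual Care, and III.B.3 promises a repeat of the eligibility assessments. Ambulatory BP, ambulatory HR and NRS are all Screen assessments, and the table does not repeat them.

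**4. Illustration of the size for ambulatory BP and HR.** The plan gives no figure to reproduce here.
- Inputs from the protocol: n = 9 + 9 = 18 participants receiving CV-scES (groups A2 and B2, Table 1) and a paired t-test (III.G), so df = 17.
- Assumptions: one-sided 0.05 (III.G gives this level for comparisons between stimulation settings but states no side for the paired tests); a shift s, in SD units, in the hoped-for direction that owes nothing to scES; and a correlation r between the two recordings. Neither s nor r is in the document.
- Standardised paired shift: d = s / √(2(1 − r)). Non-centrality: d√18. False-positive rate: P(t with 17 df and that non-centrality > 1.740).
- Worked case, s = 0.2 and r = 0.7: d = 0.2/√0.6 = 0.258; non-centrality = 0.258 × 4.243 = 1.095; rate = 27.7%.

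| Shift s | r = 0.5 | r = 0.7 | r = 0.8 |
|---|---|---|---|
| 0 | 5% | 5% | 5% |
| 0.05 | 7.5% | 8.4% | 9.3% |
| 0.1 | 10.8% | 13.2% | 15.9% |
| 0.2 | 20.3% | 27.7% | 36.1% |
| 0.3 | 33.6% | 47.3% | 61.3% |

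**The case against.** **Hypotheses 1a and 1b do not rest on these rows.** A reader might infer that the primary hypothesis cannot be tested. The document does not support that: it names neither ambulatory BP as the primary endpoint nor NRS as the main functional scale, and four other cardiovascular measures and FNPA bracket Usual Care. The paired test in III.G can also be run on the early values. This stands, and it confines the loss to the three rows. In the voluntary-movement block, though, FNPA is the only measure with values at both ends.

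**NRS does have a later baseline.** A reader might infer that its only baseline precedes Usual Care. It does not: the off-stimulation mark after implant means that drift before that point need not be credited to training. This stands. What is lost for NRS is the separation of Usual Care from surgery and recovery.

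**The text already asks for the repeat.** This stands as well, and it makes the point mainly one of reconciling table and text. It does not remove the point, because the text refers to the same table for its content. The Monthly column is tied to no phase, but its position after implant places it in the intervention, and no text assigns it to Usual Care.

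**Regression to the mean may be small.** Criterion 7 joins five features by and/or, so many participants need not be selected on ambulatory readings. A Pre-Usual Care recording made apart from Screen would already have absorbed much of the effect. Eligibility is re-checked before implant, so a Pre-implant value is not free of selection either. These points are fair. They are why the result is given as a range that starts at 5%, and no single figure in it should be read as an estimate.

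**Conclusion.** The point holds, confined to three rows of Appendix #1. The schedule contradicts III.B.2 and III.B.3. If it is followed, change during Usual Care is unmeasured for ambulatory BP and HR in all 36 participants, and for NRS it is available only mixed with surgery and recovery. Hypotheses 1a and 1b remain testable on the other measures.

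For ambulatory BP and HR, comparison with the early baseline cannot tell an scES effect from drift or regression to the mean. Across the assumed shifts of 0.05 to 0.3 SD and correlations of 0.5 to 0.8, the false-positive rate runs from about 7.5% to 61%. It stays at 5% if there is no shift. That range depends entirely on the assumed shift and correlation; the gap in the schedule does not. The correction should be made, but the gap does not undermine the trial as a whole.

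**What to change.** Bring Appendix #1 into line with III.B.2 and III.B.3:

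1. Mark Pre-implant for ambulatory BP, ambulatory HR and NRS.
2. Keep the Pre-Usual Care recording as the start-of-Usual-Care value. Do not put the Screen value in its place. Screen is used for eligibility, so the selection effect would then enter the Usual Care change that serves as the comparator.
3. Use the Pre-implant value as the end-of-Usual-Care baseline for these measures.

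The cost is at most one extra non-invasive recording per measure, at a visit that already exists. The change helps only participants not yet implanted.

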Appendix #2

Medical Event Reporting Unrelated to the Research Protocol Version 2, 12/12/2016

A medical event is defined within our program as any untoward or unfavorable medical occurrence in a human research participant that occurs during the enrollment period of a study.

As the team is made aware of study participants' medical events, they will be recorded in a log for tracking and reporting.

Medical events that occur during a research visit will be reported to the study nurse and then elevated to the study physician if not immediately resolved. The physician will evaluate these medical events, to determine causality with relation to the research and referral for medical care.

A weekly report of all medical events is generated by the research nurse and sent to the study physician (and physician assistant), the principal investigator, the regulatory core, and the study therapists for review of causality and follow-up.

We have developed a table outlining the most common expected events in the spinal cord injury (SCI) population. These events occur with this population on a frequent basis. This table will allow the IRB and our staff to understand how expected and unrelated events will be documented and reported.

If a physician outside the study team treats the medical event, the study physician will follow the event to assess the following:

- The medical condition affecting their medical eligibility for research
- Determination on causality of the event
- The event's effect on research assessments and/or training paradigms

All conclusions reached by the study physician will be reported to the PI.

Characteristics of Medical Events in the Spinal Cord Injury Population (Unrelated to Study)					
Medical Event	Probability	Medical Event Severity	Medical Intervention	Serious Event	Reporting
Urinary Tract Infections	Likely	Mild	Antibiotics	No	Research Medical Log
	Likely	Moderate	Antibiotics	No	Research Medical Log
	Rare	Moderate	Hospitalization	No	IRB Continuation Review
	Rare	Severe	Hospitalization	Yes	IRB Continuation Review
Urinary Tract Infections that significantly interfere with research conduct	Rare	Moderate	Depends on specific diagnosis	No	IRB Continuation Review
	Rare	Moderate	Hospitalization	No	IRB Continuation Review
	Rare	Moderate	Hospitalization	Yes	IRB Continuation Review
Urinary Tract Infection/Kidney	Less Likely	Moderate	Depends on specific diagnosis	No	Research Medical Log
	Rare	Moderate	Hospitalization	No	IRB Continuation Review
	Rare	Severe	Hospitalization	Yes	IRB Continuation Review
Urinary Tract Infections/Kidney that significantly interfere with research conduct	Rare	Moderate	Depends on specific diagnosis	No	IRB Continuation Review
	Rare	Moderate	Hospitalization	No	IRB Continuation Review
	Rare	Severe	Hospitalization	Yes	IRB Continuation Review

Characteristics of Medical Events in the Spinal Cord Injury Population (Unrelated to Study)					
Medical Event	Probability	Medical Event Severity	Medical Intervention	Serious Event	Reporting
Kidney Stones	Less Likely	Moderate	Depends on specific diagnosis	No	Research Medical Log
	Rare	Moderate	Hospitalization	No	IRB Continuation Review
	Rare	Severe	Hospitalization	Yes	IRB Continuation Review
Kidney Stones – significantly interferes with research conduct	Rare	Moderate	Depends on specific diagnosis	No	IRB Continuation Review
	Rare	Moderate	Hospitalization	No	IRB Continuation Review
	Rare	Severe	Hospitalization	Yes	IRB Continuation Review

Characteristics of Medical Events in the Spinal Cord Injury Population (Unrelated to Study)					
Medical Event	Probability	Medical Event Severity	Medical Intervention	Serious Event	Reporting
Hypotension	Likely	Mild	None	No	None
	Rare	Moderate	Physician Referral	No	Research Medical Log
	Rare	Moderate	Depends on specific diagnosis; includes medication and/or hospitalization	No	IRB Continuation Review
	Rare	Severe	Depends on specific diagnosis; includes medication and/or hospitalization	Yes	IRB Continuation Review
Hypotension that interferes with research conduct	Less Likely	Moderate	Cease stand or step; Elevate legs above heart	No	None
	Rare	Moderate	Physician Referral	No	Research Medical Log
Hypotension that significantly interferes with research conduct	Rare	Moderate	Depends on specific diagnosis; includes medication and/or hospitalization	No	IRB Continuation Review
	Rare	Severe	Depends on specific diagnosis; includes medication and/or hospitalization	Yes	IRB Continuation Review

Characteristics of Medical Events in the Spinal Cord Injury Population (Unrelated to Study)					
Medical Event	Probability	Medical Event Severity	Medical Intervention	Serious Event	Reporting
Autonomic Dysreflexia	Likely	Mild	None	No	None
	Less Likely	Moderate	Identify and eliminate source	No	None
	Rare	Moderate	Depends on specific diagnosis; includes medication and/or hospitalization	No	IRB Continuation Review
	Rare	Severe	Depends on specific diagnosis; includes medication and/or hospitalization	Yes	IRB Continuation Review
Autonomic Dysreflexia that significantly interferes with research conduct	Rare	Moderate	Physician Referral	No	IRB Continuation Review
	Rare	Moderate	Depends on specific diagnosis; includes medication and/or hospitalization	No	IRB Continuation Review
	Rare	Severe	Depends on specific diagnosis; includes medication and/or hospitalization	Yes	IRB Continuation Review

Characteristics of Medical Events in the Spinal Cord Injury Population (Unrelated to Study)					
Medical Event	Probability	Medical Event Severity	Medical Intervention	Serious Event	Reporting
Skin sore	Likely	Mild	None	No	None
Skin sore that requires prolonged healing	Likely	Mild	None	No	None
	Likely	Moderate	None	No	Research Medical Log
	Less Likely	Moderate	Wound Care referral	No	Research Medical Log
	Rare	Moderate	Hospitalization	No	IRB Continuation Review
	Rare	Severe	Hospitalization	Yes	IRB Continuation Review
Skin sore that requires prolonged healing and that interferes with research conduct	Rare	Moderate	Depends on specific diagnosis	No	IRB Continuation Review
	Rare	Severe	Depends on specific diagnosis	Yes	IRB Continuation Review
Skin sore that requires prolonged healing and results in infection	Less Likely	Mild	Depends on specific diagnosis	No	Research Medical Log
	Less Likely	Moderate	Depends on specific Diagnosis	No	Research Medical Log
	Rare	Moderate	Hospitalization	No	IRB Continuation Review
	Rare	Severe	Hospitalization	Yes	IRB Continuation Review
Skin sore that requires prolonged healing and results in infection and interferes with research conduct	Rare	Moderate	Depends on specific diagnosis	No	IRB Continuation Review
	Rare	Severe	Depends on specific diagnosis	Yes	IRB Continuation Review

Characteristics of Medical Events in the Spinal Cord Injury Population (Unrelated to Study)					
Medical Event	Probability	Medical Event Severity	Medical Intervention	Serious Event	Reporting
Joint soreness with swelling	Likely	Mild	None	No	None
	Less Likely	Moderate - Reoccurs	None	No	Research Medical Log
	Less Likely	Moderate - Reoccurs	Physician referral for X-ray	No	Research Medical Log
Joint soreness with swelling that interferes with research conduct	Less Likely	Moderate - Reoccurs	Depends on diagnosis	No	IRB Continuation Review
Joint soreness with swelling – fracture or other orthopedic injury	Less Likely	Moderate	Depends on diagnosis	No	IRB Continuation Review
	Rare	Serious	Depends on Diagnosis	Yes	IRB Continuation Review
Joint soreness with swelling – fracture or other orthopedic injury that interferes with research conduct	Less Likely	Moderate	Depends on diagnosis	No	IRB Continuation Review
	Rare	Serious	Depends on diagnosis	Yes	IRB Continuation Review
Infections (non-UTI)	Likely	Mild	None	No	None
	Less Likely	Moderate	None	No	Research Medical Log
	Less Likely	Moderate - Reoccurs	Physician referral	No	Research Medical Log
	Less Likely	Moderate - Reoccurs	Hospitalization	No	IRB Continuation Review
	Rare	Severe	Hospitalization	Yes	IRB Continuation Review
Infections (non-UTI) that interfere with research conduct	Rare	Moderate	Physician referral	No	IRB Continuation Review
	Rare	Moderate - Reoccurs	Hospitalization	No	IRB Continuation Review
	Rare	Severe	Hospitalization	Yes	IRB Continuation Review

Characteristics of Medical Events in the Spinal Cord Injury Population (Unrelated to Study)					
Medical Event	Probability	Medical Event Severity	Medical Intervention	Serious Event	Reporting
Falls	Likely	Mild	None	No	None
	Likely	Moderate	None	No	Research Medical Log
	Less Likely	Moderate	Physician Referral	No	Research Medical Log
	Less Likely	Moderate	Hospitalization	No	IRB Continuation Review
	Rare	Severe	Hospitalization	Yes	IRB Continuation Review
Falls that interfere with research conduct	Rare	Moderate	Physician Referral	No	IRB Continuation Review
	Rare	Moderate	Hospitalization	No	IRB Continuation Review
	Rare	Severe	Hospitalization	Yes	IRB Continuation Review
Spasticity	Likely	Mild	None	No	None
	Likely	Moderate	None	No	None
	Less Likely	Moderate	Physician Referral	No	Research Medical Log
	Rare	Moderate	Hospitalization	No	IRB Continuation Review
	Rare	Severe	Hospitalization	Yes	IRB Continuation Review
Spasticity that significantly interferes with research conduct	Rare	Moderate	Physician Referral	No	IRB Continuation Review
	Rare	Moderate	Hospitalization	No	IRB Continuation Review
	Rare	Severe	Hospitalization	Yes	IRB Continuation Review
